The risks of the proposed study primarily include discomfort and embarrassment with the pelvic examination. This risk is not unique to study participants as all new patients undergo a comprehensive pelvic floor myofascial examination. Participants may also experience discomfort or embarrassment with intravaginal tube placement. Finally, breach of confidentiality is another risk. Every precaution will be taken to ensure data are kept strictly confidential. Only the research team will have access to paper data, which will be stored in a locked cabinet in the FPMRS offices. Enrolled patients will be assigned unique study identification numbers. A password-protected electronic database will be established using REDCap, and only the research team will have access. No results will be presented in a personally identifiable manner.

2.f Early Withdrawal of Subjects

i When and How to Withdraw Subjects

Patients may request withdrawal from the study at any point. Patients who desire to withdraw from the study will need to inform the research assistant or PI via telephone or

in writing using the contact information in the consent document. Patients who elect to withdraw from the study will not be contacted about future study-related tasks.

ii Data Collection and Follow-up for Withdrawn Subjects

Data collection will stop when the patient requests withdrawal from the study. It is possible, depending on the timing of study withdrawal, that some data collection will have already occurred. This data will be used according to the protocol for data use in the study, however, no further data collection will occur. In the event that a patient withdraws and requests that her previously-collected data be destroyed and not included in the study outcomes, that will be done according to her wish.

E3 Study Intervention

3.a Description

The intervention group will be provided with one vaginal cryotherapy tube, filled with a mixture of isopropyl alcohol (2ml) and water (8ml) that has been kept in the freezer. This mixture results in a “slushy” consistency and prevents the solution from freezing solid thus decreases the risk of discomfort or injury due to the temperature of the tube. They will be instructed to store these tubes in their home freezer.

The control group will be provided with an identical tube that is empty. An empty tube was chosen as the control because a tube with room-temperature liquid may still be perceived as cold.

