Vaginal cryotherapy is recommended routinely by the physicians and physical therapists in our Division and, to date, no adverse events related to the cryotherapy have been reported. Theoretical adverse events that could be related to use of cryotherapy in the vagina include skin irritation or injury from the temperature of the tube or trauma to the vagina related to placement of the tube.

Patients will be provided with contact information for study personnel who can be reached 24/7 to report an adverse event. At the follow up visit at 2 weeks, patients will be asked whether they experienced any adverse events. Follow up questions will be asked, as appropriate, for patients reporting adverse events during the study period. Adverse events will be monitored and recorded in the REDCap database. Adverse event reporting will occur throughout the duration of the study procedure.

Each reported adverse event will be reviewed by the members of the study team and graded according to the Dindo-Clavien classification for adverse events (see table). (32). Although this classification system is designed for surgical interventions, it is the most applicable classification system currently available for the intervention proposed in this

study. Any Class II or higher complications that are related or possibly related to the study intervention will result in a temporary cessation of enrollment and an investigation by the study team. A determination as to whether the study may resume will be made by the consensus of the study team. If more than 10% of enrolled patients report Class I complications that are related or possibly related to the study intervention, a similar process will occur.

TABLE 1. Classification of Surgical Complications

Grade	Definition
Grade I	Any deviation from the normal postoperative course without the need for pharmacological treatment or surgical, endoscopic, and radiological interventions Allowed therapeutic regimens are: drugs as antiemetics, antipyretics, analgesics, diuretics, electrolytes, and physiotherapy. This grade also includes wound infections opened at the bedside
Grade II	Requiring pharmacological treatment with drugs other than such allowed for grade I complications Blood transfusions and total parenteral nutrition are also included
Grade III	Requiring surgical, endoscopic or radiological intervention
Grade IIIa	Intervention not under general anesthesia
Grade IIIb	Intervention under general anesthesia

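### The two physical harms F3 3.a names have no adverse-event item or pause trigger of their own, and milder cases fall under a pooled 10% limit whose denominator is undefined

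*Combined protocol and SAP*

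**What the plan says.** F3 3.a (Safety and Compliance Monitoring) gives the theoretical harms of the intervention as "skin irritation or injury from the temperature of the tube or trauma to the vagina related to placement of the tube". Sections 3.a and 3.d of E3 also recognise the cold hazard: the alcohol and water mixture is used partly to lower the risk of injury.

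Events are graded on the Dindo-Clavien table. Grade I is "Any deviation from the normal postoperative course without the need for pharmacological treatment or surgical, endoscopic, and radiological interventions", with an allowance for "drugs as antiemetics, antipyretics, analgesics, diuretics, electrolytes, and physiotherapy". Grade II is "Requiring pharmacological treatment with drugs other than such allowed for grade I complications". The protocol acknowledges that the scale was built for surgery and says it is the most applicable one available.

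There are two pause triggers:
- One event is enough at the higher grades: "Any Class II or higher complications that are related or possibly related to the study intervention will result in a temporary cessation of enrollment".
- Class I has a proportion limit: "If more than 10% of enrolled patients report Class I complications that are related or possibly related to the study intervention", the same process follows.

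The scheduled adverse-event question is a general one at the 2-week visit, with follow-up questions as appropriate and a contact line available at all hours. The diary items listed in E3 3.e cover timing, duration, pain and pelvic floor symptoms. No adverse-event item is listed.

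Section 2.e and the opening of F3 both begin "The risks of the proposed study primarily include discomfort and embarrassment with the pelvic examination". They add discomfort or embarrassment on placing the tube, and breach of confidentiality. Neither lists temperature injury or vaginal trauma.

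**The concern.** The protocol identifies two specific harms, but nothing in its data collection or pause rule refers to them specifically. Whether a cold injury counts as Class I or Class II depends on the treatment it needs, not on the lesion. One that heals unaided, or needs only an analgesic, is counted alongside minor complaints. The Class I limit then divides by all enrolled women, half of whom use an empty room-temperature tube and cannot have a cold injury.

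This matters because D1 says there are no outcome studies of transvaginal cryotherapy, and G2 makes adverse events the only stated ground for pausing or stopping. If cold injury is not asked about by name, described, and tabulated by arm, the trial may finish without a usable estimate of the rate of the harm specific to cold.

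**Working it through.** **Inputs.** Total enrolment is 66 (F1, G1), 33 per group (G1), allocated 1:1 (E2 2.d). G1 gives 132 as the total if no patient joins both aims. The Class I limit is strictly above 10% of enrolled patients, and no arm or time point is given (F3 3.a). Cold exposure is in the cryotherapy arm only (E3 3.d). Tube insertion is in both arms (E3 3.b).

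**The plan's own figure.** G1 reaches 33 per group from 30 and 20% loss. That does not reproduce: 30/0.8 = 37.5, so 38, and 30 × 1.2 = 36, whereas 33 = 30 × 1.10. This is a separate matter and barely affects the present point, as the 76 row below shows.

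**Largest Class I count that does not pause, judged at full enrolment.** This is the largest x with x/N ≤ 0.10, then divided by one arm.

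| N enrolled | No pause | Pause | Share if all are in one arm |
|---|---|---|---|
| 66 | 6 (9.1%) | 7 (10.6%) | 6/33 = 18.2% |
| 76 | 7 (9.2%) | 8 (10.5%) | 7/38 = 18.4% |
| 132 | 13 (9.8%) | 14 (10.6%) | 13/66 = 19.7% |

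The exact (Clopper-Pearson) 95% interval for 6/33 is 7.0% to 35.5%.

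**Running count.** If the 10% is checked as each woman enrols, with her event counted at that moment, the k-th event must come no earlier than the 10k-th enrolment. One event among the first nine women would already pause, and the sixth must fall at or after patient 60. Take six events spread at random over 66 enrolments. By the ballot formula, with 60 women without an event, the chance of never exceeding the limit is (60 + 1 − 9 × 6)/(60 + 1) = 7/61 = 11.5%. A simulation of 20,000 trials gave about 11%.

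**How much the count matters.** Assume, for illustration, Class I events only in the cryotherapy arm.

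| Assumed true rate | Chance of a pause, final 66 (at least 7 of 33) | Chance of a pause, running count (simulated) |
|---|---|---|
| 15% | 22% | 69% |
| 20% | 50% | 85% |

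The same sentence of the protocol therefore gives quite different protection depending on a reading that it does not settle.

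**The case against.** The strongest reply has five parts.

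1. **More serious injuries are covered.** One related or possibly related injury that needs a drug outside the Grade I list, or a procedure, pauses enrolment at once. This stands. A reader might infer that serious cold injury could accumulate without a pause; the documents do not support that. The gap is confined to injuries managed without such treatment.

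2. **The 18% does not come from the surgical scale.** A reader might blame the grading for it. It comes from the pooled denominator, and a lesion-based scale with the same pooled 10% limit would give the same 6 of 33. This stands. The grading decides which injuries fall under the limit, and the denominator decides how many can pass.

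3. **It is a corner case.** Every Class I event must be in the cryotherapy arm, no other related Class I event may occur, and the limit must be judged against the final 66. Any minor complaint judged possibly related uses up part of the margin. The figure also fits cold injury only, because placement trauma can occur in all 66 women. All of this stands.

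4. **The scale does not follow prescribing habit.** A reader might infer that the rule depends on what happens to be prescribed. Table 1 speaks of treatment needed or required, so that reading goes too far.

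5. **The hazards are already handled.** The team reviews each reported event, F3 3.a names both harms, the list in 2.e is worded as the primary risks only, and no adverse events have been reported in routine use. The consent pages and survey attachments are not available to this review, so it cannot be said that participants are not told of these harms or not asked about them. In part this stands. It does not change the text that can be read: a general adverse-event question, diary items with no adverse-event entry, and two risk lists that do not match 3.a.

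**Conclusion.** The point holds as a cheap improvement to safety detection. It is not a finding that the pause rule fails. Milder cases of the two named harms are Class I, are not identified separately, and fall under a pooled limit. At its worst that limit lets 6 of 33 cold-exposed women (18.2%), or 13 of 66 (19.7%) at the larger size, have such an injury without a pause.

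Those figures assume full enrolment as the denominator, all Class I events in the cryotherapy arm and none elsewhere. Under a running count, six events would escape a pause in roughly one trial in nine. The protocol does not say which applies, and that omission needs correcting in its own right.

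A reader might infer that a separate pause line, independent of grade, is required. Naming harms and grading all events on one scale are compatible, so the documents do not compel that. How the trigger should treat these harms is for the study team to decide.

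**What to change.** - Keep Dindo-Clavien for reporting.
- Add temperature injury and placement trauma to REDCap as two named items, asked by name in both arms at the scheduled adverse-event question. Describe the lesion as well as the grade, and tabulate results by arm.
- Bring 2.e and the opening of F3 into line with F3 3.a.
- Have the study team reconcile the pause rule with the harms 3.a names. The revised text should say whether the 10% uses a running or a final count, and whether the denominator is all enrolled women or those exposed to the hazard. No threshold is proposed here.

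The cost is protocol wording and two form items. Asking by name may bring in more minor reports for the team to review. Asking in both arms lets those reports be compared with control.

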All new patients presenting to our facility undergo our standardized pelvic floor myofascial examination and are asked to rate their pain on palpation of the bilateral OI and LA muscles on a 0-10 verbal pain rating scale (0=none 1-3=mild, 4-6=moderate, and 7-10=severe). Patients found to have pelvic floor myofascial pain of at least 4/10 in severity at any of the four sites will be considered eligible and approached for study inclusion. Exclusion criteria include age <18, non-English speaking, current diagnosis of dementia, limited physical mobility that would prevent full participation in pelvic floor PT, complaint or known diagnosis of chronic pelvic pain or prior use of vaginal cryotherapy. We will enroll a total of 66 patients for the trial.

F2 Schedule of Measurements

Data collection will occur at baseline and 2 weeks (**Figure 2**). Patients will complete validated questionnaires including the short forms of the Pelvic Floor Distress Inventory (PFDI-20), Pelvic Floor Impact Questionnaire (PFIQ-7), and Pelvic Organ Prolapse/Urinary Incontinence Sexual Questionnaire IUGA-Revised (PISQ-IR, 24, 25). Questionnaires will be scored according to published protocols (26, 27). (see attached)

F3 Safety and Adverse Events

The risks of the proposed study primarily include discomfort and embarrassment with the pelvic examination. This risk is not unique to study participants as all new patients undergo a comprehensive pelvic floor myofascial examination. Participants may also experience discomfort or embarrassment with intravaginal tube placement. Finally, breach of confidentiality is another risk. Every precaution will be taken to ensure data are kept strictly confidential. Only the research team will have access to paper data, which will be stored in a locked cabinet in the FPMRS offices. Enrolled patients will be assigned unique study identification numbers. A password-protected electronic database will be established using REDCap, and only the research team will have access. No results will be presented in a personally identifiable manner.

3.a Safety and Compliance Monitoring

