Grade IV	Life-threatening complication (including CNS complications)* requiring IC/ICU management
Grade IVa	Single organ dysfunction (including dialysis)
Grade IVb	Multiorgan dysfunction
Grade V	Death of a patient
Suffix "d"	If the patient suffers from a complication at the time of discharge (see examples in Table 2), the suffix "d" (for "disability") is added to the respective grade of complication. This label indicates the need for a follow-up to fully evaluate the complication.

*Brain hemorrhage, ischemic stroke, subarachnoidal bleeding, but excluding transient ischemic attacks.
CNS, central nervous system; IC, intermediate care; ICU, intensive care unit.

F4 Study Outcome Measurements and Ascertainment

The data collected will include demographic characteristics; basic medical and reproductive health histories; pre- and post-treatment myofascial examination scores; PFDI-20, PFIQ-7, and PISQ-IR results at baseline and follow up visits; PGI-I and SAPS scores at study conclusion; PFPT assessments. Demographic data, medical and reproductive health histories, and pre- and post-treatment myofascial examination scores will be obtained from the medical record. Baseline questionnaires will be completed by the patient electronically directly in REDCap using a secure, password-protected tablet owned and operated by the research team. Follow up surveys and questionnaires will be administered electronically as secure surveys built in REDCap.

G Statistical Plan

G1 Sample Size Determination and Power

We expect vaginal cryotherapy to result in at least 3-point improvement in myofascial pain scores as reported on a 0-10 verbal pain rating scale. Prior studies investigating clinically significant reductions in pain scores report greater than 2 points on a 0-10 scale or 30% reduction in pain as clinically significant²⁸. In order to detect a 3-point difference with 80% power and alpha 0.05, we would need to enroll 30 patients per group. Accounting for a 20% loss-to-follow up rate, we plan to enroll 33 patients per group for a total of 66 patients. Patients may participate in Specific Aim #1 only, in Specific Aim #2 only, or both Specific Aims. If no patients participate in both Specific Aim #1 and Specific Aim #2, then 132 patients will be required overall.

G2 Interim Monitoring and Early Stopping

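### Enrolling 33 per group does not cover the stated 20% loss to follow-up (38 are needed); at that loss the plan's own figures give about 74% power, not 80%

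*Combined protocol and SAP*

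**What the plan says.** G1 (Sample Size Determination and Power) gives the base requirement: "In order to detect a 3-point difference with 80% power and alpha 0.05, we would need to enroll 30 patients per group." The next sentence adds the allowance for loss: "Accounting for a 20% loss-to-follow up rate, we plan to enroll 33 patients per group for a total of 66 patients." G1 then says that if no patient joins both aims, "then 132 patients will be required overall", which is 2 × 66. F1 (Screening for Eligibility) repeats the total: "We will enroll a total of 66 patients for the trial."

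Three other sections matter here. G3 names a t-test or Wilcoxon rank sum test between arms for the primary outcome of each aim. G4 removes patients with a missing primary outcome from the analysis. E3, 3.b places the Aim 1 repeat examination within 10 minutes of the office treatment, while Aim 2 is assessed at 2 weeks.

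G1 gives neither a standard deviation nor the sidedness of alpha.

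**The concern.** Two adjacent sentences in G1 cannot both be right. A base of 30 with a 20% allowance does not give 33 by the correct inflation or by the usual shortcut. Because G4 analyses only patients with an observed primary outcome, each lost patient reduces the analysed sample.

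The enrolment target is the number the site will work to. If the site stops at 66 and loss is what the plan expects, the 2-week comparison runs below its stated power. A null result there would then be read against an 80% figure that the design does not deliver.

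**Working it through.** **Inputs.** From G1: 30 per group required, 80% power, alpha 0.05, 3-point difference, 20% loss, 33 per group enrolled. From G3: two-sample t-test. From G4: missing primary outcomes excluded. Two-sided alpha is assumed and then varied.

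**Step 1: try to reproduce 33.**
- Correct inflation: n / (1 − loss) = 30 / 0.80 = 37.5, so 38 per group, 76 in total.
- Common shortcut: n × (1 + loss) = 30 × 1.20 = 36 per group.
- Neither gives 33. The stated figure equals 30 × 1.10.

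**Step 2: what 33 does cover.** The largest loss that still leaves 30 is 1 − 30/33 = 9.1%.

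**Step 3: what is left at 20% loss.** 33 × 0.80 = 26.4 per group on average. If each patient is lost independently with probability 0.20, the chance that a group of 33 keeps 30 or more is 8.1%. The chance that both groups do is 0.081² = 0.7%.

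**Step 4: power at that number.** The SD is not given, so the base of 30 cannot be checked independently. Taking G1 at its word that 30 gives 80%, power depends only on the ratio of the analysed n to 30, and the SD cancels. By the normal approximation:

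power = Φ[(1.960 + 0.842) × √(n/30) − 1.960]

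- n = 26.4: 2.802 × √0.880 = 2.628, and Φ(0.668) = 74.8%
- n = 26: 2.802 × √0.867 = 2.608, and Φ(0.648) = 74.2%

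With the noncentral t, 30 per group at 80% implies a standardised effect of 0.736, that is an SD of 3/0.736 = 4.08. At that effect:

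| Analysed per group | Power (two-sided t, 0.05) |
|---|---|
| 33 (no loss) | 83.7% |
| 30 (G1's requirement) | 80.0% |
| 26.4 (mean after 20% loss) | 74.6% |
| 26 | 73.9% |

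With 38 enrolled, 38 × 0.80 = 30.4 remain and power is 80.5%.

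**Step 5: other readings of G1**, at 26 to 26.4 per group.
- One-sided alpha: about 75%.
- 30 rounded up from just above 29, two-sided: about 75 to 76%.
- The same rounding, one-sided: about 76 to 77%.

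**Step 6: the figure that inherits the error.** 132 = 2 × 66. On the same terms with 38 per group it would be 2 × 76 = 152.

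**The case against.** **The slip may be in the 20%.** Since 33 is exactly 30 × 1.10, the authors may have used a 10% allowance. At 10% loss, 33 × 0.90 = 29.7 per group remain and power is 79.6%, essentially as planned. The documents cannot settle which number is wrong. This stands as an explanation of how the error arose, but it does not remove it: either the 20% or the 33 must change.

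**The 74% is conditional.** It rests on G1's 30 being right, and the implied SD of 4.08 is back-solved, not reported. With an SD of 3, power at 26.4 per group would be about 95%. That is true, but about 16 per group would then suffice for a 3-point difference and G1's need for 30 would itself be wrong. The 74% is therefore what the plan's own figures imply, not a forecast of the trial's actual power.

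**Aim 1 has little follow-up to lose.** This stands. The power shortfall belongs mainly to Aim 2. G1, however, applies the 20% without separating the aims, and Aim 2 has its own primary outcome. For the same reason the 152 is a mechanical doubling. It also inherits a conflict between E2, where patients may join Aim 1 only or both aims, and G1, which adds Aim 2 only.

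**It is a pilot.** G2 calls it one, but the same sentence gives testing efficacy as a purpose, and G1 makes a formal power claim. The inconsistency causes no bias and does not affect the type I error; the stated power is still wrong.

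**Conclusion.** The concern holds. The 33 per group in G1 covers a loss of 9.1%, not 20%. On the plan's own requirement of 30, a 20% loss calls for 38 per group: 5 more per group, 10 more in total. No other section reconciles the figures.

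At the stated loss, power for a true 3-point difference is about 74%, so the chance of missing it rises from 20% to about 26%. This assumes that 30 per group gives exactly 80% power with a two-sided t-test at 0.05. Allowing for rounding of the 30 and for one-sided alpha, the range is about 74 to 77%. The effect is modest and concerns mainly the 2-week comparison, but the inconsistency in the trial's sample size statement is plain and needs no outside figure to show.

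**What to change.** Correct G1 so that its requirement, loss rate, enrolment and power agree.

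**Cheapest version.** Keep 33 per group and 66 in total. State that this gives 80% power if loss is at most 9%, and about 74% if loss is 20%. If 10% was the intended allowance, replace the 20% and say why 10% is expected at 2 weeks. F1 then stays as it is. The cost is a change of wording and, if the 20% stands, a less favourable stated power.

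**If 80% power at 20% loss is wanted.** Enrol 38 per group, 76 in total, and change G1 and F1 together. I4 expects about 30 new patients a month, 57% of them with qualifying pain: 30 × 0.57 = 17.1 a month. If all of them enrolled, 66 patients would take 66/17.1 = 3.9 months and 76 would take 4.4 months. The no-overlap total should be reworked only after E2 and G1 agree on whether patients may join Aim 2 alone. A plain doubling gives 152, or 8.9 months against 7.7 for 132, slightly beyond I4's upper limit of 8.

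In either case, G1 should state the SD behind the 30 with its source, say whether alpha is one- or two-sided, and say to which aim the loss allowance applies.
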